9.5.2 Statistical Considerations for Secondary Endpoints

Secondary endpoints will include a longitudinal comparison of metabolic and serological analysis (specifically measures of glucose and insulin homeostasis); the level of cognitive impairment as defined by neuropsychological testing (QDRS/CDR, MMSE, ADAS-Cog, and MoCA scores). Thresholds for reporting clinically meaningful change will include references to published minimal clinically important differences (MCIDs) for each measure. Paired samples t-tests will be used to statistically analyze each secondary endpoint, including the cognitive measures described below as well as changes in serological markers.

The ADAS-Cog evaluates participants' cognitive abilities. It is composed of 11 parts that measure word recall, object/figure naming, command following, constructional praxis, ideational praxis, orientation, word recognition, test direction recall, spoken language, comprehension, and word-finding difficulty. The ASAS-COG is scored from 0-70 by measuring the errors made in each task, with a score of 70 representing the most severe impairment. A point reduction of 3.1 to 3.8 has been found to be the minimal clinically important difference (Schrag & Schott, 2012).

The MMSE is a 30-point questionnaire that evaluates cognition. The MMSE includes specific tasks that assess orientation, attention, memory, language and visual-spatial skills. MMSE scores range from 0 – 30 possible points; 0-17: severe cognitive impairment, 18-23: mild cognitive impairment, 24-30: no cognitive impairment. A point decrease \geq 3 on the MMSE has been identified as the minimally clinically important difference (Andres, 2019).

The MoCA evaluates frontal-executive functions (e.g., verbal abstraction and mental calculation), language (e.g., confrontation naming, phonemic fluency), orientation (e.g., person, place, date, day of the week, and time), visuospatial construction (e.g., simple figure copy), divided visual attention, and immediate and delayed memory of unstructured information (Nasreddine, Phillips, Bédoré, Charbonneau, Whitehead, Collin, et al., 2005). MoCA scores range from 0-30 possible points; 26 or greater is considered to reflect normal cognitive status.

The Quick Dementia Rating Scale (QDRS) is an interview-based tool administered by study officials to participants' caregivers used to obtain observations from a consistent source (Berman, Koscik, Clark, Mueller, Bluder, Galvin et al., 2017) . The QDRS form consists of 10 categorical questions (5 cognitive, 5 functional), each with 5 detailed options depicting the level of impairment as either 0 (normal), 0.5 (mild/inconsistent impairment), 1 (mild/consistent impairment), 2 (moderate impairment), or 3 (severe impairment). Based on the conversion table outlined in [name] research (2015), total QDRS scores were converted to Clinical Dementia Rating (CDR) scale levels ranging from 0 (normal aging), 0.5 (mild cognitive impairment), 1 (mild dementia), 2 (moderate dementia), and 3 (severe dementia).

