4.2 Inclusion Criteria

In order for a subject to be considered for this study, the following criterion is required:

- Diagnosis of cognitive decline due to degenerative dementia
- Age within range of 50-89 years old
- QDRS score ranging from 1.5-12.5, with a converted Clinical Dementia Rating (CDR) score of 0.5 (mild cognitive impairment) to 1 (mild dementia)

The QDRS scale will be given to all patients; a cutoff range for QDRS scores has been specified as 1.5-12.5 to qualify patients with a clinical dementia score (CDR) of 0.5 to 1.

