6 STUDY PROCEDURES

For this Phase II open label study, all participants will be screened following acquisition of a signed, written informed consent form.

Screening will involve confirmation that all inclusion criteria and none of the exclusion criterion are met. Following confirmation of inclusion and exclusion criterion, participants will undergo baseline testing to include the following: Advanced magnetic resonance imaging (MRI) of the brain, lumbar puncture, APoE genotyping, cognitive testing, and serological analysis.

All patients will have an advanced MRI of the brain to include T1 and T2-weighted structural images, susceptibility-weighted imaging, neuromelanin, arterial spin labeling (ASL) perfusion, blood oxygen level-dependent (BOLD) at rest, diffusion tensor imaging with neurite orientation density and dispersion (DTI-NODDI), and magnetic resonance spectroscopy (MRS) of the precuneus. MRI will demonstrate if patients have tumors, hydrocephalus, subdural hematomas and other structural etiologies of cognitive decline. Having the scan completed will be required for inclusion, but no specific imaging parameters will determine inclusion. The advanced MRI of the brain will be repeated upon completion of the 3-month study intervention period.

All patients will have APoE swab testing and a lumbar puncture for A β 42 and Tau proteins for Alzheimer's Spectrum. This spinal fluid examination has been shown to be both sensitive and specific for Alzheimer's disease. Cerebrospinal fluid (CSF) studies have demonstrated good sensitivity and specificity for mild cognitive impairment (MCI) and dementia of the Alzheimer's type. MRI volumetrics, perfusion scans and MR spectroscopy have shown to be responsive to change as patients progress from MCI to dementia. The lumbar puncture is performed at entry and after completion of the study protocol. The APoE testing will only be performed at baseline.

Baseline and completion (3-month) cognitive testing will include the Quick Dementia Rating System (QDRS), estimated clinical dementia rating (CDR) scale level, Mini-Mental Status Evaluation (MMSE), Montreal Cognitive Examination (MoCA), and Alzheimer's Disease Assessment Scale (ADAS-Cog12). Upon completion of the protocol intervention, participants will also be asked to report a Global Rating of Change (GRC) score in addition to the neuropsychological testing battery.

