7 STUDY ACTIVITIES

7.1 Screening Visit & Baseline Measure Collection (Days -10 to -1)

Study Screening may take place during an initial visit with study staff to obtain the following assessments, which will be recorded in participant's source documentation/medical record and on the Case Report Form (CRF):

- Participant ID number generation
- Demographic information
- Medical history
- Vital signs
- Height, weight, and calculation of BMI
- Prior/concomitant medications (must be stabilized for 30 days prior to study entry)
- Quick Dementia Rating Scale (QDRS)
- Clinical Dementia Rating (CDR) score, derived from QDRS
- Confirming eligibility (no exclusionary criteria are met)

Baseline measure acquisition may take place over the subsequent 9 days prior to starting the active study intervention, which will include the following:

- Lumbar puncture to test for AB42 and Tau protein levels
- APoE genotyping
- Advanced brain MRI
 - T1, T2, SWI, Neuromelanin, BOLD, ASL perfusion, DTI-NODDI, MRS of the precuneus
- Cognitive examination including:
 - Montreal Cognitive Assessment (MoCA)
 - Mini-mental Status Examination (MMSE)
 - Alzheimer's Disease Assessment Scale (ADAS-Cog12)
- Blood tests for:
 - Complete blood count + diff
 - Creatinine clearance
 - Thyroid hormone panel
 - Electrolytes
 - Inflammatory markers (hsCRP, TNF α , CD4, CD8, absolute neutrophils)

- Quantitative immunoglobulins
- Total and direct bilirubin
- Hemoglobin
- ProdromeScan blood test for:
 - Phosphatidylethanolamines
 - Choline
 - Mitochondrial function

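### Sections 6 and 7.1 disagree on whether QDRS is rated again after eligibility; if 7.1 governs, the score that admits a participant is also the only baseline for QDRS/CDR change, which can then include regression to the mean

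*Combined protocol and SAP*

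**What the plan says.** Section 4.2 selects on the observed score: "a cutoff range for QDRS scores has been specified as 1.5-12.5 to qualify patients" with a derived CDR of 0.5 to 1. A diagnosis of cognitive decline due to degenerative dementia is a separate inclusion criterion.

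Section 7.1 has two lists. The first is the screening visit; it contains QDRS and the CDR derived from it, and it ends with confirmation of eligibility. The second is introduced by "Baseline measure acquisition may take place over the subsequent 9 days prior to starting the active study intervention" and names MoCA, MMSE and ADAS-Cog12, but not QDRS.

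Section 6 reads differently. It says "Following confirmation of inclusion and exclusion criterion, participants will undergo baseline testing to include the following", with cognitive testing among the items, and then "Baseline and completion (3-month) cognitive testing will include the Quick Dementia Rating System (QDRS), estimated clinical dementia rating (CDR) scale level".

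Section 7.5 repeats QDRS and CDR at the 3-month visit. Section 9.5.2 says "Paired samples t-tests will be used to statistically analyze each secondary endpoint, including the cognitive measures described below". Section 9.1 instead names MMRM for the neuropsychological family. Section 5.1.2 confirms that there is no placebo group.

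**The concern.** A score retained because it fell inside a window carries a selected measurement error. Someone just below 1.5 who happens to be rated high gets in; someone just above 1.5 who happens to be rated low does not. The same happens in reverse at 12.5. The Month 3 score has not been selected in this way, so the mean can shift between the two ratings with no change in the patients. A control arm would show the same shift and remove it by subtraction, but here there is none.

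At stake is how the QDRS and CDR changes are read. They are the only cognitive endpoints that also decide entry. If the admitting score is the baseline, the paired test need not hold its nominal error rate when the drug does nothing. The sponsor also could not say whether an observed change was inflated, masked or clean.

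**Working it through.** **Step 1: which score is the baseline?** On 7.1 there is one pre-treatment QDRS, the screening one. The visits listed in 7.3 include no QDRS, so there is one follow-up value, from 7.5. On Section 6 there is a QDRS in the battery done after eligibility. Section 9.5.2 does not say which score is meant. MMRM would not change the problem: with one follow-up and no control, it estimates the same within-person change.

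**Step 2: the plan's own figure.** Section 9.2 enrols 25 to allow for 20% attrition: 20/(1 - 0.20) = 25. This reproduces, so n = 20 is used below, with alpha 0.05 (two-sided assumed).

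**Step 3: assumptions.** The documents give no QDRS mean, SD or test-retest reliability for the source clinic. All three are assumed below, with no true mean change.

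**Step 4: closed form.** Let the screening and Month 3 scores be bivariate normal with common mean mu, SD s and correlation r. Put a = (1.5 - mu)/s and b = (12.5 - mu)/s. Then

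E[change | admitted] = -(1 - r) × s × [φ(a) - φ(b)] / [Φ(b) - Φ(a)].

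- mu = 3, s = 5, r = 0.8: a = -0.3, b = 1.9. The ratio is (0.3814 - 0.0656)/(0.9713 - 0.3821) = 0.536. The change is -0.2 × 5 × 0.536 = -0.54. The SD of change is 3.05, so the standardised change is -0.176 and the noncentrality is -0.176 × √20 = -0.79. False improvement is 11.2%, against a nominal 2.5%. With r = 0.9 the change is -0.27 and the rate 7.5%.
- mu = 7, the midpoint of the window: a = -1.1, b = 1.1. The numerator is zero, so the change is 0 and the two-sided error stays at 5.0%.
- mu = 12.5, s = 5, r = 0.8: a = -2.2, b = 0. The ratio is (0.0355 - 0.3989)/(0.5000 - 0.0139) = -0.748 and the change is +0.75. False worsening is 18.0%. With r = 0.9 these are +0.37 and 10.8%.

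The normal model allows negative scores, which QDRS does not. With half-point scoring and a floor at 0, the first case falls from -0.54 to -0.38. The low-end closed-form figures are therefore on the high side.

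**Step 5: simulation closer to the scale.** True severity is gamma, with normal rating error, half-point scoring, a true 3-month change of SD 1 and mean 0, reliability 0.8 to 0.9, and n = 20. The third column also requires a true score of at least 1.5, as a stand-in for the diagnosis criterion.

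| Clinic mean / SD | False improvement (nominal 2.5%) | Same, true score at least 1.5 |
|---|---|---|
| 2 / 2 | 9.2 to 15.6% | 4.0 to 5.7% |
| 3 / 3 | 9.3 to 13.7% | 4.5 to 6.3% |
| 3 / 2 | 5.2 to 7.7% | not tabulated |
| 5 / 4 | 5.7 to 7.1% | 4.0 to 5.0% |

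The spurious change is -0.18 to -0.41 points for the 2/2 and 3/3 clinics and -0.16 to -0.30 for 5/4. With the diagnosis stand-in, the 2/2 clinic gives -0.06 to -0.15. At 8/5 it is about zero. At means 12 to 14 with SD 6 it is +0.34 to +1.13, with false worsening of 7.0 to 21.5%.

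**Step 6: re-rated baseline.** If change is taken from a second rating made after eligibility, with error independent of screening, the bias is at most 0.05 points and total rejection is about 5% in every scenario.

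**The case against.** The strongest reply is that the plan already contains the remedy. Section 6 puts QDRS in the testing that follows confirmation of eligibility, and Section 9.4 describes CDR as gathered at baseline and at final follow-up. The study events table in Appendix 1 was not in the text available for this review and may settle the matter. This stands: it cannot be said that QDRS is rated only once before treatment, only that Sections 6 and 7.1 disagree and that 9.5.2 does not name the score.

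A reader might go further and infer that the design manufactures apparent benefit on QDRS. The documents do not support that. The window cuts both tails, and no passage describes the clinic's QDRS distribution. The net effect may favour the drug, cancel, or count against it.

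The low-end error rates are also sensitive to the assumptions. They are driven largely by people whose true score is below 1.5, many of whom the diagnosis criterion should keep out, and a narrower clinic spread lowers them too. The high-end figures need a clinic averaging 12 to 14, where only about 45 to 59% would qualify.

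Finally, QDRS/CDR is one of several secondary measures in an open-label, uncontrolled trial, where tenths of a point on a 0 to 30 scale are a small part of the uncertainty. That argues for low severity. It does not remove the need to say which score is the baseline.

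**Conclusion.** The point holds as a conditional one of low severity. Sections 6 and 7.1 conflict on whether QDRS is rated again after eligibility. If 7.1 is what staff carry out, the QDRS/CDR paired change can include regression to the mean that the analysis cannot separate from a drug effect.

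For a mostly mild clinic the size is about -0.05 to -0.4 points, with false improvement of about 4 to 15% instead of 2.5%; the lower part of that range, about 4 to 6%, applies if the diagnosis criterion excludes true scores below 1.5. The bias is about zero near a clinic mean of 7 to 8 and turns into apparent worsening if many patients lie above 12.5. These figures rest on assumed reliability of 0.8 to 0.9, assumed clinic distributions, 20 completers and no true mean change. The documents fix neither sign nor size.

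The finding should not be extended to other endpoints. The primary MRI measures are not selected on, and MoCA, MMSE and ADAS-Cog12 are collected after screening, so they could be touched only through their correlation with QDRS.

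**What to change.** In 7.1, add QDRS and its derived CDR to the baseline list after eligibility is confirmed, alongside MoCA, MMSE and ADAS-Cog12. This brings 7.1 into line with Section 6; check that Appendix 1 agrees. In 9.5.2, state that QDRS and CDR change is measured from this post-eligibility score and that the screening score is used for eligibility only. The second rating must not act as another entry test, or the selection returns.

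The cost is one more short caregiver interview for each of about 25 participants, within the existing 9-day window, and one sentence in each section. Two limits remain. Error shared by two ratings a few days apart is not fully removed, and a cleaner baseline does not replace a control arm for other non-drug changes.

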9.6 Safety Analysis

Mild, moderate and severe adverse effects/reactions and mortality will be monitored to confirm the safety and tolerability of NE3107 in the study population. Blood tests and

clinical monitoring will be performed according to standard practice for these agents. Participants will be discontinued if they have moderate or severe adverse reaction ratings according to the ICH SAE E2A. Unexpected or excess serious adverse reaction and excess mortality will result in early termination of the study. Suspected unexpected serious adverse reactions, life threatening reactions and mortality will be reported to the FDA by way of the primary IND holder (Biovie, Inc.) as required under 21 CFR 312.32(c)(1)(v). These reports will be recorded in a lab notebook that will be locked away in a cabinet requiring a key that only the study staff will have access to. This information will also be transcribed to a computer file that will be kept behind username and password.

10.2 Institutional Review Board (IRB) Approval

Prior to study initiation, institutional review board (IRB) approval shall be obtained and proof shall be provided to all regulatory agencies. The IRB submission for NE3107-TRP-001 “A Phase II Open Label Study for the Use of Anti-Inflammatory, Insulin Sensitizing NE3107 for the Treatment of Cognitive Decline Due to Degenerative Dementias” is awaiting final review and approval from Advarra IRB (Pr#00058626). All reviews and approval by the IRB will be in accordance with Good Clinical Practice (GCP).

In the event of any serious adverse events, the IRB will be notified by the study sponsor.

10.3 Ethical Conduct of the Study

All aspects of this trial shall be conducted in compliance with all applicable federal, state, and local laws and regulations. In particular, the study protocol will be conducted in accordance with generally accepted standards of good clinical practice, informed consent for human participants, and conflict of interest policies related to conduct in clinical research. The Principal Investigator will be responsible for the conduct of the study and oversight of the clinical research staff, all of whom will remain in full compliance with the protocol.

10.4 Participant Information and Consent

The clinical research staff shall obtain from each participant, prior to screening or official entry in the study protocol, a signed informed consent and necessary authorization to disclose health information to BioVie in a form approved in writing by the IRB. The principal investigator, all sub-investigators, and the research coordinator may obtain consent from the participant. In obtaining and documenting informed consent, the investigator will comply with the applicable regulatory requirements and will adhere to good clinical practice and the ethical principles that have their origin in the Declaration of Helsinki. The written informed consent form and any other written information provided to participants will be revised whenever new information becomes available that may be relevant to the participant’s consent. Any revised written informed consent form and written information will receive IRB approval in advance of use. Neither the investigator, nor the study staff, will coerce or unduly influence a patient to participate or continue participation in a trial. All consenting will be done behind closed doors in the privacy of a medical exam room. The participant will be allowed to take home the consent form if he/she needs more time to review the document. The participant will be read the consent form out loud by the member of the study staff

obtaining consent. As part of the study criteria, the participant will be required to be cognitively aware and understand the English language. Therefore, the participant's consent should be viewed as their own, and without any undue influence or coercion. If the participant feels uncomfortable, he/she may have an impartial witness of their choice enter the room for the consenting process.

Before signing the consent form, the member of the study staff obtaining consent will verbally ask the participant if he/she has any questions regarding the consent form. If the participant says no, the member of the study staff will ask if all information in the consent form was understood. If the participant says yes, then a member of the study staff will ask if the participant consents to being in this study. If the participant says yes, he/she is ready to sign the consent form.

As stated in the Process of Consent section, all consent by the participant will be done behind closed doors in a private medical exam office. Once the participant has agreed to be in the study and has signed the consent form, the documentation will exist both physically and electronically. The consent form will be scanned into a computer in which it will be stored under the appropriate folders designated for this research study. The computer will be locked under username, password, and firewall, and will only be accessible by the study staff. The physical version of the consent form will be stored behind lock and key in a drawer or cabinet designated for this research study. The key will also only be accessible by the study staff.

10.5 Participant Confidentiality

All participant data will be protected and kept private during the study in compliance with federal, state, and local regulations. All documentation collected by the study staff and Sponsor will be kept confidential. The name and identity of the participants will remain confidential. Any physical data, such as a lab notebook used to record data during the study, will be kept under lock and key. Any digital data will be kept under username and password. Both physical and digital data will only be accessible by the research staff.

The study staff and sponsor shall comply with applicable laws and regulations, as amended from time to time, including without limitation, the Health Insurance Portability and Accountability Act of 1996 and its implementing regulations (HIPAA) with respect to the collection, use, storage, and disclosure of Protected Health Information (PHI) as defined in HIPAA. All study-related PHI shall be collected, stored, used, accessed, and disclosed only as permitted by the IRB-approved informed consent form or HIPAA authorization form obtained from a study participant. BioVie's ability to review participants' study-related information contained in the study participants' medical records shall be subject to reasonable safeguards for the protection of study participant confidentiality and the study participants' informed consent forms or HIPAA authorization forms. BioVie shall not attempt to identify, or contact, any Study participant unless permitted by the informed consent form or HIPAA authorization form.

10.6 Study Monitoring

The primary investigator, [name], is responsible for monitoring the study site and study activities. [name] is on staff at Providence Saint John's Medical Center which is within one to two miles of the clinical site of [name] MD, Inc. dba The Regenesis Project at [name]. The clinical site has five on-campus physicians with Advanced Cardiovascular Support certification and a crash cart, resuscitation equipment and a nursing staff including an RN which are all on site.

All participant data will be recorded on-site at The Regenesis Project. All participant data will be kept private, and all post-processing will be done internally.

The Principal Investigator will assign internal audits to be performed at least twice per month for the duration of the study protocol.

